
III. STUDY OBJECTIVES

To test Perception Threshold Tracking (PTT) and multi-level MRI as methods for early detection and grading of severity of neuropathy in patients with diabetes mellitus.

To use multi-level MRI for characterization of peripheral and central nervous system changes related to neuropathy in patients with diabetes mellitus.

To compare Perception Threshold Tracking (PTT) and MRI to methods of traditional clinical practice and established methods of clinical research like Corneal Confocal Microscopy (CCM) and Quantitative Sensory Testing (QST) as well as axon flair-mediated neurogenic vasodilation (AF).

To test reliability of different measurements of neuropathy.

A better understanding of the underlying neuropathy of diabetes and new methods for early, reliable detection of DPN could result in intensified treatment and prophylactic measures prolonging of the complicationfree period of diabetes mellitus. Ultimately, this could potentially result in fewer complications related to the diabetic foot, and maybe even prolonged overall-survival and reduced healthcare cost.

IV. METHODS

A. Study Design

This study is a prospective, observational, cross-sector study starting March 1, 2019 running until December 1, 2021. The study will be conducted on patients from Aalborg University Hospital. Participants will be informed about the trial both written and vocally and no changed in antidiabetic medication will be performed. The instruments will include Corneal Confocal Microscopy (CCM), Quantitative Sensory Testing (QST), axon flair-mediated neurogenic vasodilation (AF), handheld heart rate measurement device (Vagus[™]), cuff, and MRI, which are all established methods of clinical research. Furthermore, participants will be tested using monofilament and Biothesiometry, which equals actual clinical practice, and with Perception Threshold Tracking (PTT), which is a new take on an older, well-known technology. Further tests will include a handheld pinprick device, measurements of peripheral arterial disease (PAD) and conventional NCS. The main endpoint of the study will be sensitivity/specificity of all examinations, as well as a comparison of the newer methods against more well-established modalities.

B. Study Population

The study population include four well-defined groups of subjects:

- 1. Patients with Type 1 diabetes and painful diabetic peripheral neuropathy (DPN).

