- 2. Patients with Type 1 diabetes and non-painful diabetic peripheral neuropathy (DPN)
- 3. Patients with Type 1 diabetes and without diabetic peripheral neuropathy (DPN).
- 4. Healthy control subjects matched for age, BMI, and gender.

Diabetes duration, HbA1c, insulin use, ethnicity, and co-morbidities will be matched between group 1, 2 and 3 to best ability.

Inclusion criteria:

- 1. Men and women minimum 18 years of age and maximum 70 years of age
- 2. Signed informed consent form
- 3. Diagnosed with diabetes type I (for group 1-3)
- 4. Diagnosed with DPN defined as a threshold above 25-volt biothesiometry or absent feeling on the big toe using 10g-monofilament. (for group 1-2)
- 5. Answered questionnaire: PainDETECT
- 6. Nothing abnormal on initial tests (group 4)
- 7. Accepted initial screening blood samples
- 8. MRI-compatible participant

Exclusion criteria:

1. Current or previous alcohol- or drug abuse

- 2. Abnormal screening blood samples
- 3. Not being able to understand Danish written and/or verbally
- 4. Not being able to corporate to examination (e.g. not being able to speak, suffering from senile dementia etc.)
- 5. Previous chemotherapy or intake of experimental medicine
- 6. Active HSV- or VZV-infection or known HIV
- 7. Known severe skin disease
- 8. Known neural damage or disease in the neural system (e.g. MS, Guillain-Barre etc.)
- 9. Critical limb ischemia defined as in current clinical consensus[63]
- 10. Allergy or intolerance to histamine or inability to make do without for one day
- 11. Pregnancy
- 12. Active cancer-disease

C. Assessment of Resources

The study will be conducted in collaboration with Steno Diabetes Center Northern Denmark (SDCN) and Department of Radiology, Aalborg University Hospital. SDCN has access to patients with diabetes and can provide the necessary premises.

The study will be conducted in collaboration with Center for Neuroplasticity and Pain (CNAP), Aalborg University and SDCN, who have the technical and financial resources needed to establish the setup and conduct the examinations. Furthermore, an experienced research Bio. Med. Lab. Technologist is signed for the project thereby, alongside the Ph.D.-students, ensuring trained personnel. The study is set for a long inclusion, but additional time is available if required, as the Ph.D.-students are employed until 31st of October 2022.

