This mainly include biothesiometry and 10g-monofilamnent as these simple measures equals current clinical standard when screening for neuropathy. In biothesiometry, the detection limit of vibration is determined with slow rising strength until the patient perceives the vibration. In 10g-monofilament testing the physician uses a thin nylon fiber, which bends at a pressure of 10 grams. The filament is applied to four specific spots at the bottom of the foot. The tests are usually conducted during the scheduled visit to the outpatient clinic. If not, these tests will be performed just after inclusion before other experimental tests. This point also includes measurements of blood pressure measured at the arm, leg and toe as well as oxygen pressure in the blood vessels of the toe (TPO₂). This allows a good assessment of potential PAD. Results from the clinical examination might be collected as a Neuropath Disability Score (NDS). Above mentioned examinations might be conducted at any of the later mentioned sessions (see appended flowchart).

Estimated time: 15-20 min (possibly partly conducted during already scheduled appointment).

512 mN pinprick

This is a small custom-made pinprick device based on standardized QST (see below) principles. The device functions much like the monofilament described above but differs since it has a sharp finish thereby activating not large- but small nerve fibers. This test is conducted either during the scheduled visit or just after inclusion in the study alongside clinical examination.

Estimated time: 5 min.

Conventional nerve conduction

Will be conducted by the department of Neurophysiology, Aalborg University Hospital, as "golden standard" for assessment of large nerve fiber function. The test is a standard clinical test and might already be conducted at the time of inclusion.

Estimated time: 30 min.

Corneal Confocal Microscopy

Corneal Confocal Microscopy (CCM) is a noninvasive method for studying of the human cornea in vivo. It is used in an increasing fashion for assessment of corneal small nerve fiber pathology as an expression of peripheral neuropathy[46]. Before examination, the eye of the participant will be anaesthetized using 0.4% benoxinate hydrochloride and Viscotears for front eye lubrication. The examination will be conducted by personnel trained by seasoned international operators.

Estimated time: 60 min.

Quantitative Sensory Testing

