Stimulus–response-functions for dynamic mechanical allodynia (ALL) are determined using a set of three light tactile stimulators: a cotton wisp (force: 3 mN), a cotton wool tip fixed to an elastic (force: 100 mN), and a standardized brush (force: 200–400 mN). The three tactile stimuli are applied five times each with a single stroke of approximately 1–2 cm in length over the skin. They are intermingled with the pinprick stimuli in randomized order and subjects are asked to give a rating on a scale equal to the one used for MPS (see above).

5) Wind-up ratio: the perceptual correlate of temporal pain summation for repetitive pinprick stimuli

In this test of temporal summation, the perceived magnitude of a single pinprick stimulus is compared with that of a train of 10 pinprick stimuli of a force of 256 mN repeated at a rate of one prick per second. Subjects are asked to give a pain rating representing the pain at the end of the train using the same scale as for MPS and ALL (see above). Single pinprick stimuli are alternated with a train of 10 stimuli until both are done five times at five different skin sites on the same foot. The mean pain rating of trains divided by the mean pain rating to single stimuli is calculated as wind-up ratio (WUR)

6) Vibration detection threshold

Vibration detection threshold (VDT) is tested using a tuning fork (64 Hz) placed over the medial malleolus. Vibration threshold is determined by the mean of three series of descending stimulus intensities.

7) Pressure pain threshold

This test is performed using a pressure gauge device able to deliver a pressure up to 200 N/cm². The pressure pain threshold (PPT) is determined with three series of ascending stimulus intensities on m. tibialis ant., each applied as a slowly increasing ramp of 50 kPa/s.

Estimated time: 60-90 min.

Axon flair-mediated neurogenic vasodilation

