To avoid 'mass significance' a combined analysis of all measurements will be performed by logistic regression models (LRM) in three steps. This will allow an estimate of the odds ratio and accuracy of each of the measurements and the measurements in combination. First, a series of univariate LRM will be performed for each measurement to investigate the odds ratio and accuracy of the individual. Second, a multiple factor LRM with all measurements as factors will be performed to estimate the odds ratio and accuracy for all measures in combination. Thirdly, factor reduction will be performed to assess the accuracy and odds ratio of a set of independent measures.

Simple bivariate correlation will be performed to further investigate the relation between measurements. Due to the complexity of the measurements a further analysis of the interdependency of the measures using factor analysis will be performed.

VII. DATA AND SAFETY MONITORING PLAN

The project will be reported to the Data protection Agency (DPA), and all sensitive data will be stored in either Red-CAP or on the protected server of Aalborg University Hospital, *"Elektronisk system adgang"* (ESA).

Data are stored in accordance with the stipulations in The Danish Personal Data Protection Act (Persondataloven) and other relevant Danish legislation. If any data processing would occur in foreign countries, the data will be anonymized and handled according to the Danish Data Protection Act.

The data can only be used for the interpretation of this project and will therefore not be of interest to third party.

The project is included in "Region Nordjyllands fællesfortegnelse".

VIII. STUDY LIMITATIONS

Both PTT and QST require corporation from the patients and include subjective measures of pain. As the measured thresholds are not purely objective, psychosocial factors might influence test results.

The study includes diabetic patients exclusively and might not be applicable on populations with different causes of neuropathy.

The expected number of participants are set at 80, thus maybe require additional larger studies to confirm findings.

IX. ETHICAL CONSIDERATIONS

A. Informed Consent

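### DPN status is set by two participant-report tests, so accuracy against group status can tilt the comparison towards PTT and QST detection thresholds, by an unknown amount

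*Combined protocol and SAP*

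**What the plan says.** Section IV.B, inclusion criterion 4, gives the only definition of DPN: "Diagnosed with DPN defined as a threshold above 25-volt biothesiometry or absent feeling on the big toe using 10g-monofilament". Section IV.D (Clinical examination) describes biothesiometry: "the detection limit of vibration is determined with slow rising strength until the patient perceives the vibration". The monofilament criterion is likewise a report of not feeling.

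Section IV.A sets the goal: "The main endpoint of the study will be sensitivity/specificity of all examinations", together with "a comparison of the newer methods against more well-established modalities". Section VI.B plans ANOVA across the four groups, then logistic models, of which it says: "This will allow an estimate of the odds ratio and accuracy of each of the measurements and the measurements in combination". It does not name the outcome of those models, so the reference standard for accuracy is left implicit.

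PTT is read from a button press and release. QST includes touch detection with von Frey filaments, and for vibration: "Vibration detection threshold (VDT) is tested using a tuning fork (64 Hz) placed over the medial malleolus". These are the same two modalities that define DPN. Conventional nerve conduction is also collected and is presented in section IV.D as the golden standard "for assessment of large nerve fiber function. The test is a standard clinical test". It has no part in the DPN definition.

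Section VIII warns about subjectivity for PTT and QST only: "As the measured thresholds are not purely objective, psychosocial factors might influence test results".

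**The concern.** As worded, section VIII treats subjectivity as a handicap of PTT and QST. If the reference has the same weakness, it can work as an advantage. A participant with a cautious criterion for saying that a stimulus is felt is more likely to exceed 25 V, to miss the monofilament, and to have high PTT and QST detection thresholds, whatever the state of the nerves. Reference and index test then err together. CCM, MRI, axon flare and nerve conduction are not read from a reported perception threshold, so they gain nothing from that agreement.

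At stake is the comparative half of the main endpoint. A reader who sees PTT ahead of CCM or MRI against group status could not tell better detection of nerve damage from agreement between two participant reports. This is separate from scoring the two defining tests against themselves, and from examiner expectation.

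**Working it through.** The plan gives no figure for this point, so there is none to reproduce. The check is whether the mechanism produces a gap between methods of equal true validity, and how large.

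**From the documents.** 20 participants per group, so groups 1-3 hold 3 × 20 = 60: 40 with DPN and 20 without. The background puts DPN at around 20% in type 1 diabetes.

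**Assumed, not in the documents.** The share s of error variance due to response style, and the loading k of PTT on the reference's response style (1 = same exposure, 0 = none).

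**Model.** True large-fibre loss L ~ N(0,1). Shared response style C has variance s·v. Every test has the same total error variance v = 0.75, so each correlates with L at 1/√1.75 = 0.76.
- Reference: R = L + C + e, positive above its 80th percentile
- PTT: P = L + kC + e
- Objective test O and nerve conduction N: L + e

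The mechanism shows in the correlations with the reference: corr(O,R) = 1/1.75 = 0.57, whereas corr(P,R) = (1 + k·s·v)/1.75. The ROC gaps (PTT minus objective, against group status) come from simulation.

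| s | k | corr(P,R) | ROC gap |
|---|---|---|---|
| 0 | any | 1/1.75 = 0.57 | 0 |
| 0.10 | 1 | 1.075/1.75 = 0.61 | 0.02 |
| 0.20 | 1 | 1.15/1.75 = 0.66 | 0.04 |
| 0.33 | 1 | 1.2475/1.75 = 0.71 | 0.07 |
| 0.50 | 1 | 1.375/1.75 = 0.79 | 0.11 |
| 0.33 | 0.5 | 1.124/1.75 = 0.64 | 0.03 to 0.04 |
| 0.33 | 0 | 1/1.75 = 0.57 | 0 |
| 0.33 | -0.5 | 0.876/1.75 = 0.50 | -0.04 |

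The half-loading row is about half the full-loading gap: 0.5 × 0.07 = 0.035. With v from 0.5 to 1.0 and s from 0.10 to 0.50 at full loading, the gap runs from 0.015 to 0.127.

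**Nerve conduction as reference, same patients.** corr(P,N) = corr(O,N) = 1/1.75 in the source population. After sampling by group the gap stays within 0.01.

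**A second model.** True status is binary. Reference status comes from an either-or rule on two perception tests, each with a 10% false-positive rate. True ROC area is 0.86 for both methods and two thirds have DPN. With a shared fraction of within-status variance of 0, 0.1, 0.2, 0.3 and 0.5, the apparent areas (PTT-like versus objective) are 0.71 v 0.71, 0.74 v 0.71, 0.76 v 0.70, 0.79 v 0.70 and 0.85 v 0.69. Over true areas of 0.76 to 0.92 and DPN shares of 0.5 to 0.67, the gap is about 0.02 to 0.21 for shared fractions of 0.1 to 0.5. It is zero at zero.

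**Scale.** With 40 v 20 and an area A = 0.80, the Hanley-McNeil variance uses Q1 = 0.8/1.2 = 0.667 and Q2 = 2(0.64)/1.8 = 0.711. SE = √[(0.16 + 39 × 0.0267 + 19 × 0.0711)/800] = 0.056. A gap of 0.03 to 0.11 is thus roughly half to two standard errors of a single area.

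**How plausible full loading is, by procedure.** Biothesiometry ascends only. QST thermal ramps also end on a press, so slow reporting pushes both towards abnormal. PTT averages readings from rising and falling intensity, so delay partly cancels. Von Frey thresholds use ascending and descending series. QST vibration uses descending intensities, where late reporting lowers the threshold and looks better. The wind-up ratio divides one rating by another, so rating style may largely cancel.

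**The case against.** The strongest reply is that the bias is conjecture. The documents give no shared variance, and the upper figures assume that PTT carries the full response style of the reference. The procedures above speak against that for several measures, and with negative loading the sign reverses. This stands: the claim has to be conditional and limited to detection thresholds. It does not remove the point, because a cautious criterion, unlike mere slowness, would act in the same direction in rising and falling series.

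Three stronger readings are tempting, and the documents do not support them.
- A reader might infer that PTT and QST accuracy is inflated outright. In the second model the PTT-like area mostly stayed below its true value; the objective test was marked down further. The distortion is relative.
- A reader might infer a raised risk of a false significant win for PTT. Section VI.B contains no pairwise ROC test, so there is no such error rate to inflate.
- A reader might infer that stepwise selection will keep PTT. The text describes three modelling steps ending in factor reduction, and names no stepwise rule.

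It can also be said that the plan already admits the poor sensitivity of clinical tests, and already correlates all measurements and runs a factor analysis. But error in the reference that is not shared marks equally valid methods down alike (gap 0 at s = 0). Correlations and factor analysis do not give sensitivity or specificity against nerve conduction.

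**Conclusion.** The point holds in conditional form. The structure is documented: the only DPN definition rests on participant report, the main endpoint compares perception-based with objective methods, and section VIII leaves out the defining tests. Whether and how far this tilts the comparison is unknown. Under the main model the ROC-area gap runs from 0 to about 0.11 in favour of perception-based detection thresholds, is about 0.03 to 0.04 at a 33% share with half loading, and could reverse for measures such as QST vibration. The second model gives larger gaps at the top of its range.

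All of this assumes that accuracy is judged against criterion 4. That is the natural reading, since no other DPN definition is given, but section VI.B does not say so. Naming the reference is therefore part of the repair.

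**What to change.** In section VI.B, state that accuracy is reported within groups 1-3 against two references:
1. group status under criterion 4;
2. as a sensitivity analysis, the nerve conduction result, either normal/abnormal or amplitude as a continuous value, without scoring nerve conduction against itself.

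Add that where the order of perception-based and objective methods differs between the two references, in either direction, this is reported and superiority is not claimed from group status alone. The rule should be symmetric. Requiring only perception-based methods to win under both references would cost power on one side and is not needed.

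In section VIII, extend the sentence on subjective thresholds to biothesiometry and monofilament.

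The cost is a few lines of text and one further run of the analyses on data already planned, with no added visits or tests. The downside is that nerve conduction drops out as an index test in the second analysis. That reference also reflects large fibres only, so it is not neutral for small-fibre methods (CCM, axon flare, pin-electrode PTT), and the report should say so.

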that stanks har smertersme i gennemsnit været indon for de mende 2 upp? 0 1 2 3 4 5 7 8 0 npen overal mølige overal mølige overal mølige 0 <t< td="">u 1 2	3 4 3		and the second s	1 1	G	</t<>	u 1 2	3 4 3		and the second s	1 1	G
med lette udsving Konstante smerter med smerteanfaid Smerteanfaid, ingen smerter mellem enfaldens Hyppige smerteantaid, med smerter mellem enfaldens Hvis ja: marker mellem enfaldens Hvis ja: marker mellem enfaldens Skel ikke meget lint Kar du en kriblende efter prikkende fornemmelse i det område, hvor du primært har smerter (f.eks. som myrekryb eller elektrisk enurren)? skel ikke meget lint Kar du en kriblende efter prikkende fornemmelse i det område, hvor du primært har smerter (f.eks. som myrekryb eller elektrisk enurren)? skel ikke meget lidt Kar du en kriblende efter on dyne i det område, hvor du primært har smerter, som elektriske statt? skel ikke meget lidt Kidt meget lidt idt moderal meget lidt idt meget lidt idt ske ikke meget lidt meget lidt idt meget lidt idt meget lidt idt meget lidt idt meget l	saneste 2 uger? 0 1 2 ngen Sæt kryds v	3 4 5 red det billade, d	6 7 8	tar de 9 10 ærst mulige		243
Smerteenfald, ingen smerter Hyppige smerteenfald, med Hyppige smerteenfald Hypige smerteenfald		med lette uds Konstante sm	ving		K N	
Hyppige sinkreatrate, ineit Hvis ja: marker med en pil, i hvilken retring din smerter mellem anfaldens Lider du af en brændende fornemmelse i det område, hvor du primært har smerter (f,eks, som brændenælder)? meget lidt Skel ikke meget lidt int i Har du en kritelende eller prikkende fornemmelse i det område, hvor du primært har smerter (f,eks, som myrekryb eller elektrisk enurren)? meget i meget i Skel ikke meget lidt ict i moderal meget i meget i Er let børering f,eks, ef tøj eller en dyne i det område, hvor du primært har smerter, smerter/smeget i meget i meget i Har du pludselige smerteanfald i det område, hvor du primært har smerter, som elektriske stød? meget i meget i Har du pludselige smerteanfald i det område, hvor du primært har smerter, som elektriske stød? meget i meget i Fremkalder kukte eller varme f,eks, af vand i et badekår, af og til smerter i det område, hvor du primært har smerter? meget i meget i sket ikke meget lidt lidt moderat meget i meget i Fremkalder kukte eller varme f,eks, af vand i et badekår, af og til smerter i det område, hvor du primært har smerter? meget i meget i sket ikke meget lidt lidt moderat meget i meget i 	Smerteanfald,				g til endre områder af	Smerteanfald,				g til endre områder af
brændenælder)? skel likke in meget lint in krit in moderat ingelig Har du en kribbende efter prikkende fornemmelse i det område, hvor du primært har smerter (fjeks, som myrekryb eller elektriek anurren)? slat ikke in megel lidt in ict in moderat in meget ingelig Friet berering f.eks. af tøj eller en dyne i det område, hvor du primært har smerter, smerterludd? slat ikke in meget lidt indt indt in moderat in meget ingelig Har du pludsellige smerteanfald i det område, hvor du primært har smerter, som elektriske stød? slat ikke in meget lidt indt indt in moderat in meget indet område, hvor du primært har smerter, som elektriske stød? slat ikke in meget lidt indt indt indt indt indt indt indt i	-			The second	ja: marker med en p	oil, i hvilken retning dine
Skel likke meget lint ktt moderat meget { rigtig meget { Har du en kriblende eller prikkende fornemmelse i det område, hvor du primært har smerter (f.eks. som myrekryb eller elektrisk enurren)? rigtig meget { rigtig meget { slet ikke meget lidt { ict i moderat { meget { rigtig meget { Er lat berering f.eks. af føj eller en dyne i det område, hvor du primært har smerter, smerterfutd?? rigtig meget { rigtig meget { Har du pludsellge smerteanfald i det område, hvor du primært har smerter, som elektriske stad? rigtig meget { rigtig meget { Fremkalder kukke eller varme f.eks. af vand i et badekar, af og til smerter i det område, hvor du primært har smerter? meget { rigtig meget { slet ikke megel lidt { lidt { moderat { meget { meget { meget lidt { lidt { moderat { meget { meget { meget { slet ikke { megel lidt { lidt { moderat { meget { meget { meget { slet ikke { meget lidt { lidt { moderat { meget { meget { meget { slet ikke { meget lidt { lidt { moderat { meget { meget { m	Lider du al en b	rændende fornem	melse i det områd	le, hvor du primært	har amerter (f,eks	BOM
Har du en kriblende eller prikkende fornemmelse i det område, hvor du primært har smerter (f.eks. som myrekryb eller elektriek anurren)? rigtig sløt ikke megel ildt lidt moderal meget Er let berøring f.eks. af tøj eller en dyne i det område, hvor du primært har smerter, smerterkuld? rigtig meget sløt ikke meget lidt lidt uoderat meget rigtig sløt ikke meget lidt lidt uoderat meget rigtig sløt ikke meget lidt lidt uoderat meget rigtig Har du pludselige smerteanfald i det område, hvor du primært har smerter, som elektriske stød? rigtig meget rigtig sløt ikke megel lidt lidt moderat meget rigtig Fremkalder kukte eller varme f.eks. af vand i et badekar, af og til smerter i det område, hvor du primært har smerter? rigtig meget meget sløt ikke megel lidt lidt moderat meget meget meget Fremkalder kukte eller varme f.eks. af vand i et badekar, af og til smerter i det område, hvor du primært har smerter? meget meget meget meget me	_ '		ett 🗖	modecat 🗔	menet	
myrekryb eller elektrisk sinurren)? slat ikke megel IIdt ikt er lat berering f.eks. af tøj eller en dyne i det område, hvor du primært har smerter, smertefukd?? slat ikke meget IIdt ikt meget IIdt ikt meget IIdt ikt meget IIdt ikke meget IIdt ikt meget IIdt ikt 	• –					• –				
satisfield meger indit not initial end of an initial initinitial initial initial initial initinitinitial initial i						100
skit ikke meget lidt ikit unoderat meget rigig meget Har du pludsellige smerteanfald i det område, hvor du primært har smerter, som elektriske statt? nigtig meget nigtig meget nigtig meget slet ikke meget lidt lidt moderat meget nigtig meget Fremkalder kukle eller varme f.eks. af vand i et badekar, af og til smerter i det område, hvor du primært har smerter? meget lidt lidt moderat meget nigtig meget nigtig meget Har du nedsat følesans i det område, hvor du primært har smerter? nigtig meget nigtig meget nigtig meget nigtig meget Har du nedsat følesans i det område, hvor du primært har smerter? nigtig meget nigtig meget nigtig meget Har du nedsat følesans i det område, hvor du primært har smerter? nigtig meget nigtig meget nigtig meget Har du nedsat følesans i det område, hvor du primært har smerter, f.eks. med en finger, smerter? nigtig meget nigtig meget Fremkalder et let tryk i det område, hvor du primært har smerter, f.eks. med en finger, smerter? nigtig meget nigtig meget slet ikke meget lidt lidt moderat meget nigtig meget slet ikke meget lidt lidt	slet ikke 🗔	megel lidi 🗖	iett 📋	moderal 🗔	meget 🗋	
set ikke meget iidt iidt meget meget Har du pludselige smerteanfald i det område, hvor du primært har smerter, som elektriske stød? neget neget slet ikke meget lidt iidt moderal meget neget Fremkalder kulde eller varme f.eks. af vand i et badekar, af og til smerter i det område, hvor du primært har smerter? neget nigtig slet ikke meget lidt lidt moderal meget nigtig slet ikke meget lidt lidt moderal meget <td< td="">Er let berøring (	f.eks. af løj eller en	dyne i det områd	le, hvor du primært	har smorter, smort	and the second se	</td<>	Er let berøring (f.eks. af løj eller en	dyne i det områd	le, hvor du primært	har smorter, smort	and the second se
Har du pludsellige smerteanfald i det område, hvor du primært har smerter, som elektriske støtt? slet ikkemegel lidtlidtmoderalmeget	- Internet Contraction	meget lidt 🔲	Tielt 🗖	moderat 🗌	meget 🔲	mgbg
siet ikke meget intt intt intoterat meget meget Fremkalder kulde eiler varme f.eks. af vand i et badekar, af og til smerter i det område, hvor du primært har smerter? intt meget rigtig slet ikke meget lidt ist moderat meget meget rigtig slet ikke meget lidt ist moderat meget meget meget slet ikke meget lidt list moderat meget meget meget slet ikke meget lidt list moderat meget meget meget slet ikke meget lidt list moderat meget meget meget slet ikke meget lidt list moderat meget meget meget slet ikke meget lidt lidt moderat meget meget meget (Udfyldes af lægen) lidt moderat meget meget meget meget slet ikke meget ikdt lidt moderat meget meget meget meget slet ikke meget ik	Shat ikke 🛄	-				
Fremkalder kukle eiler varme f.eks. af vand i et badekar, af og til smerter i det område, hvor du primært har smerter? rigtig sket ikke i megel lidt i lidt i lidt i moderat i meget i meget i meget i meget i ingtig rigtig Har dv nedsat følesans i det område, hvor du primært har smerter? meget i ingtig sket ikke i megel lidt i lidt i lidt i moderat i meget i meget i meget i ingtig meget i ingtig sket ikke i megel lidt i lidt i lidt i moderat i meget i meget i meget i meget i ingtig meget i ingtig Fremkalder et let tryk i det område, hvor du primært har smerter, f.eks. med en finger, smerter? ngtig skel ikke i meget lidt i lidt i moderat i meget i meget i meget i meget i it. ngtig skel ikke i meget lidt i lidt i lidt i moderat i meget i meget i rigtig meget i variaties af lægen) neget i idta i meget i rigtig meget skel ikke i meget lidt i lidt i variaties af lægen meget i rigtig meget i variaties af lægen	_	ge smerteanfald i o		du primært har sme	rter, som elektrisk	e zpan s
sist inke meger indit	Har du pludsell	· _	let område, hvor d		The second second second	dgtig
Har dv nedsat følesans i det område, hvor du primært har smerter? rigtig slet ikke meget lidt i idt moderat meget meget i Fremkalder et let tryk i det område, hvor du primært har smerter, f.eks. med en finger, smerter? rigtig slet ikke meget lidt i idt moderat meget i slet ikke meget lidt i idt moderat meget i slet ikke meget lidt i idt moderat meget i (Udfykkes af lægen) idt moderat meget i slet ikke meget idt i idt moderat meget i x 0 = 0 x 4 = x 5 =	Har du pludsell slet ikke 🗌 Fremkalder kul	imegel lidt 🗋	iet område, hvor o lidt 🗌	moderal 🗌	meget 🗌	hgtig meget
see inke meget lot meget meget Fremkalder et let tryk i det område, hvor du primært har smørter, f.eks. med en finger, smørter? meget meget slet ikke meget dl lidt moderat meget slet ikke meget idl lidt moderat meget	Har du pludsell slat ikka 🗌 Fremkalder kul smorter?	megel lidt 📑 de eiler vanne f.eks	det område, hvor o lidt 🗋 s. af vand i et bad	moderal 🗌 ekar, af og til smert	meget 🗌 er i det område, hv	ngtig meget vor du primært her rigtig
Fremkalder et let tryk i det område, hvor du primært har smerter, f.eks. med en finger, smerter? slei likke megei lidi lidi moderat megei megei slei likke megei kil lidi moderat megei megei slat likke megei kil lidi moderat megei megei slat likke megei kil lidi moderat megei megei slat likke megei kil lidi moderat megei rigitg megei slat likke megei kil lidi moderat megei stat	Har du pludsell slet ikke 🗌 Fremkalder kul smørter? slet ikke 🛄	meget lidt 📑 de eller varme f.eks meget lidt 📑	det område, hvor d lidt [] s. af vand i et bad lidt []	moderal 🗌 ekar, af og til smert moderat 🗌	meget 🗌 er i det område, hv	ngtig meget vor du primært her rigtig
stat ikke meget RdL iddt indderati, j meget L stat ikke meget RdL Idd moderat meget x 0 = 0 x 1 = x 2 = x 3 = x 4 = x 5 ±	Har du pludsell slet ikke 🗌 Fremkalder kul smørtør? slet ikke 🛄 Har du nedsat f	megel lidt [] de eller varme f.eks megel lidt [] jølesans i det områ	det område, hvor d lidt - s. af vand i et bad lidt - de, hvor du prima	moderal ekar, af og til smert moderat ert har smorter?	meget 🗌 er i dot område, hv meget 🗌	rigtig meget vor då primært har rigtig meget
(Udfyldes af lægen) slat ikke megel kill lidit moderal meget rigitg meget x 0 = 0 x 1 = x 2 = x 3 = x 4 = x 5 ±	Har du pludsell slatikke [] Fremkalder kul smørtør? slatikke [] Har du nedsat f slatikke []	megel lidt () de eller varme f.eks megel lidt () jølesans i det områ meget lidt ()	det område, hvor d lidt [] s. af vand i et bad lidt [] de, hvor du prima lidt []	moderal ekar, af og til smert moderat ert har smorter? moderat	meget - er i det område, hv meget - meget -	rigtig meget vor då primært her rigtig meget [] meget []
x0= 0 x1= x2= x3= x4= x5=	Har du pludsell slatikke [] Fremkalder kul smørter? sløtikke [] Har du nedsat f sletikke [] Fremkalder et b	megel lidt [] de eller varme f.eks megel lidt [] jelesans i det områ meget lidt [] et tryk i det område	det område, hvor d lidt s. af vand i et bad lidt de, hvor du primar lidt a, hvor du primar	moderal ekar, af og til smert moderat ert har smorter? moderat thar smorter, f.eks.	meget [] er i det område, hv meget [] meget [] meget []	hgtig meget rigtig meget meget rigtig meget rigtig
	Har du pludsell slat ikke Fremkalder kul smørtør? slat ikke Har du nedsat f alet ikke Fremkalder et b alet ikke	megel lidt [] de eller varme f.eks megel lidt [] iølesans i det områ meget lidt [] et tryk i det område meget lidt []	det område, hvor d lidt s. af vand i et bad lidt de, hvor du primær lidt lidt (Udfy	moderal ekar, af og til smert moderat moderat moderat thar smerter, f.eks. moderat wides af lægen)	meget [] er i det område, hv meget [] meget [] med en finger, sn meget []	rigtig meget rigtig meget rigtig meget rigtig meget rigtig meget
Samlet antal point ud af 35	Har du pludsell slet ikke Fremkalder kuk smørtør? slet ikke Har du nedsat f slet ikke Fremkalder et b slet ikke	megel lidt de eller varme f.eks megel lidt } iølesans i det områ meget lidt et tryk i det område meget lidt	det område, hvor d lidt s. af vand i et bad lidt de, hvor du prima lidt lidt (Udfy lida	moderal ekar, af og til smert moderat ert har smerter? moderat thar smerter, f.eks. moderat vides af lesgen) moderat	meget er i det område, hv meget meget med en finger, sn meget meget	dgtig meget rigtig meget rigtig meget rigtig meget meget rigtig meget

PD-Q = Denmark/Dennal - Final version + 25 Jun 07 - Mapi Research Institute. Werkeholikulaspagar/101-aaspi0/04/ioj_ensionigelascer.gene/2562007

o:	Patient: Efternavn:		Fornavn:	
1	Angiv antal point for a Antal poir		naet om smørter:	
			geme vedrørende smerte det endelige antal point:	
	nstante amerter d lette udsving	0		
	nstanta smerter med erteanfald	-1	hvis markenst, eller	
	erteanfald, ingen smerter liem anfaldene	+1	hvis markeret, eller	
	opige emerteerifelid, med erter mellem anfædene	+1	hvis markeret	
For	planter smerterne sig?	+2	hvis ja	
